VerifyNow Point-of-care Testing: The VerifyNow System is a turbidimetric based optical detection system which measures platelet induced aggregation as an increase in light transmittance (Accumetrics, San Diego, CA) and will be utilized according to manufacturer's instructions [23]. The assay is based on microbead agglutination and uses specific reagents for the pathways of interest. The instrument measures this change in optical signal and reports results in P2Y₁₂ Reaction Units (PRU). High on-treatment platelet reactivity (HPR) is defined by PRU >208 [4].

Study Endpoints and Determination of Sample Size:

The primary endpoint is the non-inferiority in platelet reactivity, measured as PRU, at 24 hours or hospital discharge (whichever comes first) of prasugrel versus ticagrelor among LOF allele carriers in each cohort. Under the assumption of 0 difference in mean PRU between treatments and a common standard deviation of 50 PRU, a sample size of 60 patients will allow for the 95% CI to stay within ± 40 PRU with a 85% power and $\alpha=0.025$. Considering a 25% rate of invalid results due to hemolysis or drop-out (based on our prior experience), we will randomize a total of 80 patients to ensure complete data for analysis. Non-inferiority will be assessed using a 95% CI of the difference in mean PRU between the 2 groups. Secondary endpoints will include: differences in PRU between prasugrel and ticagrelor at 30 minutes, 2 hours, and 1-4 weeks (during maintenance therapy); rates of HPR at all study time points. Subgroup analyses will be performed according to baseline antiplatelet therapy (aspirin alone vs. DAPT with aspirin and clopidogrel)

Statistical Analysis:

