Continuous variables will be expressed as a mean \pm SD or median [IQR] as appropriate. Categorical variables will be expressed as frequencies and percentages. Comparisons between continuous variables will be performed using Student t-test or Wilcoxon rank-sum test. Comparisons between categorical variables will be performed using McNemar test or binomial exact test. Missing data will not be imputed. An analysis of covariance method with a general linear model, with treatment as the main effect and baseline values of platelet reactivity as a covariate, will be used to evaluate the primary endpoint as well as all between-group comparisons at each time point. Least squares mean (LSM) differences in PRU between groups and the corresponding 2-sided 95% CI for the difference will be obtained based on the analysis of covariance model. The PD population will include all patients with PD data and without a major protocol deviation thought to affect significantly the PD effects of ticagrelor or prasugrel. The PD population will be used for analysis of all primary and secondary PD variables. Erroneously treated patients (e.g., those randomized to one treatment but actually given the other) will be accounted for based on the actual treatment received. Statistical analysis will be performed by our group using SPSSv24.0 software (SPSS Inc. Chicago, IL).

Possible Discomforts and Risk

In clinical trials, the most common clinical side effects of prasugrel were blurred vision, dizziness, headache, nervousness; infrequent events included intracranial hemorrhage (0.79%) and severe neutropenia (< 0.1%). The most important adverse effect associated with the use of prasugrel is bleeding [11]. The risk of non-surgical bleeding is 2.4%. On the other hand, the most common clinically side effects of ticagrelor were dyspnea (13.8%), headache (6.5%), cough (4.9%), dizziness

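### The primary ANCOVA discards a valid 24-hour PRU when the baseline PRU is invalid; a missing-baseline rule and one sensitivity analysis would be a cheap improvement

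*Combined protocol and SAP*

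**What the plan says.** The Statistical Analysis section sets one missing-data rule: "Missing data will not be imputed". The same section specifies an ANCOVA "with treatment as the main effect and baseline values of platelet reactivity as a covariate, will be used to evaluate the primary endpoint", and applies it to every other between-group comparison, one time point at a time. The 24-hour contrast and its two-sided 95% CI are least squares means from that model.

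On who is analysed: "The PD population will include all patients with PD data and without a major protocol deviation". What counts as having PD data is not defined by time point.

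The section on endpoints and sample size states that "a sample size of 60 patients will allow for the 95% CI to stay within ± 40 PRU" "with a 85% power" at α = 0.025, assuming no true difference and an SD of 50 PRU. It then continues: "Considering a 25% rate of invalid results due to hemolysis or drop-out", and randomises 80 so that data for analysis will be complete.

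The Blood sampling section schedules five samples: baseline (before PCI and before the loading dose), 30 minutes, 2 hours, 24 hours or discharge if earlier, and 1–4 weeks. The 30-minute and 2-hour values are secondary endpoints. Neither analysis section gives a rule for a missing baseline, a missing-data assumption or a sensitivity analysis.

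**The concern.** The primary model needs two valid samples per patient, and haemolysis can spoil either. A patient with a good 24-hour result and no usable baseline has PD data, and so appears to belong to the PD population, yet cannot enter the model. The information lost is the primary outcome itself, for want of a covariate that serves only to sharpen the comparison. The plan admits a patient through its population definition and removes the same patient through its model, without saying so.

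The reverse case is a patient with a valid baseline and early samples but a spoiled 24-hour sample. That patient adds nothing to the 24-hour estimate, although the 30-minute and 2-hour values carry some information about it. If the chance of losing the 24-hour sample were related to early platelet response, nothing in the plan would show it. Adding patients replaces numbers; it does not test that possibility.

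**Working it through.** **1. The plan's own figures.** Inputs from the sample size section: margin 40, SD 50, difference 0, α = 0.025 (read as one-sided, to match the 95% CI), power 85%, loss 25%. For non-inferiority with 30 per arm, SE = 50 × √(2/30) = 12.91, and the non-central t gives 86.1% power (29 per arm gives 84.9%). So 60 reproduces exactly. Inflation: 60 / (1 − 0.25) = 80, also correct.

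**2. Valid 24-hour result, missing baseline.** Let m be the share of patients with a valid 24-hour PRU whose baseline is invalid, and r the baseline to 24-hour correlation. The documents give neither, so both are assumed. In units of outcome variance per patient:

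- complete-case ANCOVA: variance ∝ (1 − r²) / (1 − m)
- baseline filled with a pooled mean: variance ∝ 1 − r²(1 − m)
- ratio = (1 − r²) / [(1 − m)(1 − r²(1 − m))]

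| r | m = 5% | m = 10% |
|---|---|---|
| 0.2 | 0.96 / (0.95 × 0.962) = 1.050 | 0.96 / (0.90 × 0.964) = 1.107 |
| 0.3 | 0.91 / (0.95 × 0.9145) = 1.047 | 0.91 / (0.90 × 0.919) = 1.100 |
| 0.5 | 0.75 / (0.95 × 0.7625) = 1.035 | 0.75 / (0.90 × 0.775) = 1.075 |

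This approximation ignores what the stratum explains of baseline PRU. Simulation of the two analyses gave complete-case variance 4–6% higher at m = 5% and 9–11% higher at m = 10%, with both estimates unbiased. Filling the baseline is safe here because the sample is drawn before the loading dose and the fill value is the same in both arms of a stratum.

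On the CI scale at SD 50, half-width = 1.96 × 50 × √(4/N). This is 25.3 PRU at N = 60, 26.0 at 57 (5% fewer) and 26.7 at 54 (10% fewer). The widening is about 0.7 and 1.4 PRU.

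**3. Missing 24-hour result, early samples present.** Let R² be the share of 24-hour variance that the earlier samples explain beyond treatment and baseline (assumed). In the best case, where all 25% lack only the 24-hour value, variance ∝ R²/80 + (1 − R²)/60.

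| R² | Effective N | CI half-width (PRU) |
|---|---|---|
| 0 | 60 | 25.3 |
| 0.10 | 61.5 | 25.0 |
| 0.25 | 64.0 | 24.5 |
| 0.50 | 68.6 | 23.7 |

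The gain is 0.3 to 1.6 PRU, and less if some of these patients also lack the early samples.

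**4. Bias.** Simulation of 80 patients, 4,000 runs per scenario, baseline correlation 0.5 and about 25% of 24-hour values missing (all assumed except the 80 and the 25%):

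- loss at random, or related to 2-hour PRU in the same way in both arms: complete-case bias within 0.4 PRU
- loss related to 2-hour PRU in opposite directions by arm (deliberately extreme): bias of about 5, 9 and 12 PRU at partial correlations 0.3, 0.5 and 0.7. Using the 2-hour value brought it within 0.4 PRU.

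**The case against.** **The loss is already paid for.** The plan inflates 60 to 80 expressly to secure complete data, and the natural reading is that 60 complete patients remain. That stands. A reader might infer that the 85% power is not delivered, because baseline failures come on top of the 25%. With 57, 54 or 51 complete patients, power at SD 50 would be 84.3%, 82.2% or 80.0%. The documents do not support this: the 25% is not split by sample or by cause, so adding baseline failures to it is a choice of reading. Those figures also take no credit for baseline adjustment. If 50 is the raw SD (the plan does not say), the residual SD is 50√(1 − r²), and power for 57, 54 and 51 becomes 85.7%, 83.7% and 81.5% at r = 0.2, or 92.9%, 91.5% and 89.9% at r = 0.5.

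**ANCOVA is a sound primary analysis.** That also stands. A reader might infer that it should give way to a repeated-measures model, since a simulation can show 18–26% more variance for the complete-case analysis. That result rests on assumed correlations, a covariance treated as known, and more loss than planned: 0.9 × 0.9 × 0.85 = 0.69 complete, or 31% lost. The replacement would need an unstructured 5 × 5 covariance (15 parameters) in about 80 patients, and would treat a sample taken at 24 hours or discharge as one fixed visit. It is a trade-off, not a correction.

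**Bias is hypothetical.** A reader might infer a bias of 5–7 PRU from arm-dependent drop-out. No section supports such a mechanism. Haemolysis has no stated link to PRU, and early discharge does not lose the primary sample because the sample is then taken at discharge. The two drugs' listed side effects differ (dyspnoea at 13.8% appears for ticagrelor only), which makes differential loss conceivable but does not establish it before 24 hours.

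**The early samples are not ignored.** They are secondary endpoints; only the 24-hour estimate makes no use of them.

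One escape does not work. The sample size section says "Non-inferiority will be assessed using a 95% CI of the difference in mean PRU between the 2 groups", which alone would need no baseline, but the Statistical Analysis section takes that interval from the baseline-adjusted model.

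**Conclusion.** The point holds as a cheap improvement. Followed literally, the no-imputation rule together with the baseline covariate removes patients whose primary outcome was validly measured, and the plan has no analysis that would reveal loss related to early response. The size is modest: about 4–6% extra variance if 5% of baselines are invalid and 9–11% if 10% are, or roughly 0.7 to 1.4 PRU of CI half-width against a 40 PRU margin. These rates and the correlations are assumptions; the actual number of patients affected cannot be derived from the documents. The planned power is not shown to fail, no bias is shown, and the primary model need not be replaced.

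**What to change.** Keep the ANCOVA as the primary analysis and make two changes to the Statistical Analysis section before unblinded data are examined.

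1. Narrow the no-imputation rule to outcomes. State that a missing or invalid baseline PRU will be replaced by the mean baseline PRU of the patient's randomisation stratum (aspirin alone, or aspirin plus clopidogrel), pooled over both arms. Report how many values were filled, by arm.
2. Prespecify one sensitivity analysis: a likelihood-based repeated-measures model on all scheduled PRU values (SPSS MIXED), reporting the 24-hour treatment contrast and its 95% CI beside the ANCOVA result. Name the covariance structure and a simpler fallback in case it does not converge.

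The cost is a few sentences and one extra model run in software already named, with no new samples or visits. The downsides are a covariance structure estimated in about 80 patients and reliance on a missing-at-random assumption, both acceptable in a sensitivity analysis.

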Patients scheduled for left heart catheterization (LHC) with intent to undergo PCI will be screened for the study. Patients will be screened in our inpatient and outpatient services referring patients to our cardiac catheterization laboratories to undergo LHC. Patients must fulfill all specific inclusion and exclusion criteria described below. A rapid genetic testing using the point-of-care genotyping (*Spartan RX*) will be performed in these patients to define carriers of LOF alleles. In particular, this point-of-care assay enables assessment of the following alleles: *1,*2,*3 and *17. The most common LOF alleles are *2 and *3. Therefore, carriers of *2 or *3 LOF carrier status [homozygotes (*2/*2, *3/*3 or *2/*3) or heterozygotes (*1/*2, *1/*3, *2/*17, *3/*17)] will be eligible for randomization. Patients who are non-carriers of LOF alleles (*1/*1, *1/*17 or *17/*17) will not be eligible for randomization and considered as screen failures and treated per standard of care. Also, screened patients with CYP2C19 LOF alleles who do not undergo PCI will be considered as screen failures and treated per standard of care.

Screened patients, either on aspirin monotherapy or on dual antiplatelet therapy (DAPT) with aspirin and clopidogrel as per standard of care, defined to be carriers of LOF and undergoing PCI will be randomized. Patients will be randomly (1:1 randomization) assigned to receive FDA approved doses of either prasugrel (60 mg loading dose - 10 mg/day maintenance dose) or ticagrelor (180 mg loading dose - 90 mg b.i.d maintenance dose). Randomization will be stratified according to baseline antiplatelet therapy (aspirin alone vs. DAPT with aspirin and clopidogrel). Loading dose administration will be given immediately after PCI as per standard of care. Maintenance dose will be

maintained for up to 30 days. Afterwards, patients will continue with the antiplatelet therapy recommended by the treating cardiologist (clopidogrel, prasugrel or ticagrelor).

Study Population

• Inclusion criteria:

1. Patients scheduled for left heart catheterization and undergoing PCI
2. Age 18-75 years
3. On aspirin (81mg) monotherapy or on DAPT with aspirin (81mg) and clopidogrel (75mg) as per standard of care
4. Presence of at least one 2C19 LOF allele

[figure not shown]
• Exclusion criteria:

1. Known allergies to aspirin, prasugrel, ticagrelor, or clopidogrel
2. Age >75 years
3. Weight <60kg
4. Considered at high risk for bleeding

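### The primary ANCOVA omits the randomisation stratum (baseline antiplatelet therapy), so the non-inferiority interval may be slightly wider than it needs to be

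*Combined protocol and SAP*

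**What the plan says.** - **Research design:** allocation is 1:1, and "Randomization will be stratified according to baseline antiplatelet therapy (aspirin alone vs. DAPT with aspirin and clopidogrel").
- **Statistical Analysis:** the primary endpoint and the between-group comparisons at every time point use an ANCOVA "with treatment as the main effect and baseline values of platelet reactivity as a covariate". The least squares mean difference and "the corresponding 2-sided 95% CI for the difference will be obtained based on the analysis of covariance model".
- **Study Endpoints and Determination of Sample Size:** non-inferiority is judged on a 95% CI for the difference in mean PRU. The stratification variable returns only here, for secondary use: "Subgroup analyses will be performed according to baseline antiplatelet therapy".
- **Sample size, same section:** the calculation is made "Under the assumption of 0 difference in mean PRU between treatments and a common standard deviation of 50 PRU". On that basis the plan claims 85% power with 60 evaluable patients against limits of 40 PRU in either direction. Eighty patients are randomised to allow for 25% loss.

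The plan does not put the stratum in the primary model or say why it is left out. It gives no PRU difference between strata, no expected stratum proportions and no block size. It does not say whether the 50 PRU is a total or a within-stratum SD.

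**The concern.** Stratified allocation balances baseline therapy between the arms, so the treatment estimate is already largely protected from differences between strata. An analysis that ignores the stratum still counts those differences as noise. The estimate stays unbiased, but its model-based standard error is too large and the CI is conservative.

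Baseline PRU is in the model and may stand in for the stratum, since one stratum takes a P2Y12 inhibitor before the loading dose and the other does not. The loss therefore depends on the stratum difference in post-dose PRU that remains at a given baseline PRU, called D below. If D is zero, nothing is lost. At stake is some precision and power for the non-inferiority decision. A false claim of non-inferiority does not become more likely.

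**Working it through.** **1. The plan's own figure.** Inputs from Study Endpoints and Determination of Sample Size: margin 40 PRU, SD 50, true difference 0, power 85%, α = 0.025 (read as one-sided, which matches the 2-sided 95% CI).

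n per arm = 2 × [50 × (1.960 + 1.036) / 40]² = 28.06, rounded up to 29, or 58 in total. The plan states 60, and 60 / 0.75 = 80, so the stated size reproduces. At 30 per arm the t-based non-inferiority power is 86.1%.

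**2. Simple formula.** With equal strata, and baseline PRU carrying none of the stratum effect:

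- residual variance without the stratum = within-stratum variance + 0.25 × D²
- CI half-width = t × residual SD × √(2/30), with t on 57 df without the term and 56 df with it

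If 50 is the total SD, the half-width without the term is 2.002 × 50 × 0.2582 = 25.85 PRU. With the term:

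- D = 20: residual SD = √(2500 − 100) = 48.99; half-width 25.34 (2% narrower)
- D = 40: residual SD = √(2500 − 400) = 45.83; half-width 23.70 (8% narrower)

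**3. Allowing for baseline PRU as a proxy.** Assume a 60 PRU baseline gap between strata and a within-stratum baseline SD of 50. The share of stratum variation that baseline PRU captures is 0.25 × 60² / (50² + 0.25 × 60²) = 900 / 3400 = 26%. At D = 40 the residual variance without the term is 2100 + 400 × 0.735 = 2394, against 2100 with it. The gain is 1 − √(2100/2394) = 6.3%, before the small cost of the extra, correlated term.

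**4. Simulation of the base case.** There were 4,000–10,000 trials per scenario: 80 randomised in blocks of 4 within strata (block size assumed), 60 analysed after random 25% loss, equal strata, 60 PRU baseline gap, no within-stratum relation of baseline to outcome, total SD 50.

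| Assumed D (PRU) | Change in mean CI width from adding the stratum | Power, without vs with | Type I error at a true difference of 40, without vs with |
|---|---|---|---|
| 0 | 0.5% wider | 85.5 vs 85.3% | 2.5 vs 2.5% |
| 10 | none | – | – |
| 20 | 1.2% narrower | 85.6 vs 86.4% | 2.7 vs 2.5% |
| 30 | 3.1% narrower | – | – |
| 40 | 6.0% narrower (50.9 to 47.9 PRU) | 88.2 vs 91.2% | 2.1 vs 2.4% |

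The Monte Carlo standard error of the type I error is 0.16 points, so the 2.7% is compatible with 2.5%. At D = 40 the narrowing is (50.9 − 47.9)/2 = 1.5 PRU per limit. Coverage without the term rises from 94.8% at D = 0 to 95.7% at D = 40. With the term it is about 95% throughout. Repeat runs at D = 40 gave power of 87.4–88.2% without the term and 90.2–91.2% with it.

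**5. Sensitivity.** Across equal or 75:25 strata, with or without the baseline gap, the gain is 0.8–1.8% at D = 20 and 4.7–8.4% at D = 40. With a baseline slope of 0.3 it is 1.1–2.0% and 6.3–9.4%. At D = 60, which exceeds the margin and serves only as an outer bound, the base-case gain is 16%.

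**6. If 50 is the within-stratum SD.** Power without the term is 84% at D = 20 and 82% at D = 40, against 85% with it. Part of that shortfall arises simply because the total SD then exceeds 50: √(2500 + 400) = 53.9 at D = 40.

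**The case against.** The strongest case against is that no loss has been shown. Baseline PRU is taken before the loading dose and is a direct readout of P2Y12 inhibition, which is what separates the strata, so it may carry most or all of the stratum effect. At D = 10 the term does nothing, and at D = 20 it adds less than one point of power. A 6% gain needs a residual difference as large as the whole non-inferiority margin. The common SD is most naturally read as common to the two treatment arms, and on that reading planned power is met without the term. The pre-specified model errs in the safe direction, nothing in the documents requires stratification factors in the model, and this is a feasibility study.

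All of that stands, and it limits the point to an optional suggestion. It does not remove it: the documents cannot show that D is zero, and the variable was judged important enough to stratify on and to define subgroups.

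One dependency remains. The primary endpoint is defined for each cohort, and cohort is not defined. If that meant a separate primary analysis within each therapy group, the stratum would be constant in each and the point would not arise. The single sample size of 60 analysed and 80 randomised, and the separate sentence on subgroups, favour a pooled analysis.

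**Conclusion.** The point holds as a minor one. The primary model does not reflect the stratified randomisation, and any stratum difference not explained by baseline PRU makes the non-inferiority interval conservative. In the base case the excess width is about 1% for an assumed residual difference of 20 PRU and 6% for 40 PRU. If there is none, adding the term makes the interval 0.3–0.5% wider.

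The size rests on assumed values for the residual difference, the stratum proportions, the baseline gap and the block size, and on a pooled primary analysis. Validity is not in question and the sample size need not change. Power falls below plan without the term only if 50 PRU is the within-stratum SD.

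**What to change.** Pre-specify the ANCOVA as PRU = treatment + baseline PRU + baseline antiplatelet therapy stratum (aspirin alone or DAPT), for the primary endpoint and every post-dose PRU time point. Take the least squares mean difference and its 2-sided 95% CI from that model. In the same edit, confirm that the primary analysis pools the strata by defining or removing the reference to cohorts.

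The cost is one model term, one degree of freedom and, if the stratum has no residual effect, a CI about 0.3–0.5% wider. The variable is already collected for randomisation and for the subgroup analyses. The change should be made before outcome data are seen, because a term added later could be challenged as post hoc.

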(4.5%), and nausea (4.3%), principally. Also, the most important adverse effect associated with the use of ticagrelor is bleeding [10]. The risk of non-surgical bleeding is 2.8%. All clinical events, if they were to occur, including myocardial infarctions both fatal and non-fatal, strokes, peripheral vascular disease, bypass surgery (coronary or peripheral vascular), repeated hospitalizations, and bleeding will be recorded. Clinical events will be evaluated by a local committee, comprised of 3 faculty members (2 cardiologists and 1 non-cardiologist), not directly involved in the research. In the event of a report of a serious adverse event (major bleeding – defined as life-threatening: fatal, symptomatic intracranial hemorrhage, leading to a drop in hemoglobin of at least 5 g/dL, significant hypotension requiring intravenous inotropes, requiring surgical intervention, or requiring transfusion of 4 or more units of blood; non–life-threatening: substantially disabling, intraocular bleeding leading to vision loss, or requiring at least 2 units of blood; thrombocytopenia $<50,000$), the local committee will meet and antiplatelet treatment will be withdrawn.

Definition of Adverse Events

An adverse event is any unintended or undesirable experience that occurs during the course of the clinical investigation whether or not it is considered to be therapy related. This includes any newly occurring event or previous condition that has increased in severity or frequency since the initiation of study treatment. Adverse events will be followed until resolution while the patient remains on-study. Once the patient is removed from study, events thought to be related to the study therapy will be followed until resolution or until the patient starts a new treatment regimen.

Serious Adverse Events (SAE): An adverse event occurring while on study and considered related (reasonable possibility that the study treatment caused the adverse experience) to the study treatment that results in any of the following outcomes:

- Death
- A life-threatening adverse experience.
- A persistent or significant disability, incapacity, or is a congenital anomaly, or birth defect.
- Requires inpatient hospitalization, or prolongation of existing hospitalization.

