The definition of serious adverse event also includes ‘important medical event’. Medical and scientific judgment should be exercised in deciding whether expedited reporting is appropriate in other situations, such as important medical events that may not be immediately life-threatening or result in death or hospitalization but may jeopardize the patient and/or may require medical or surgical intervention to prevent one of the other outcomes listed in the definition above. These should also usually be considered serious. Examples of such events are intensive treatment in an emergency room or at home for allergic bronchospasm; blood dyscrasias or convulsions that do not result in hospitalization; or development of drug dependency or drug abuse.

Possible benefits

The present investigation is aimed to evaluate the PD differences between ticagrelor and prasugrel in patients with CYP2C19 LOF alleles. Although, this study is not designed to evaluate differences in clinical outcomes, the results obtained may prompt further large scale clinical investigation.

Potential Financial Risks

None

Potential Financial Benefits

None

Conflict of Interest

[name] is a consultant for Bristol Myers Squibb/Sanofi-Aventis, the makers of clopidogrel (Plavix), Eli-Lilly/Daiichi-Sanyo, the makers of prasugrel (Effient), and Astra Zeneca, the makers of ticagrelor (Brilinta).

References:

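### The SAE definition requires relatedness to study treatment for all four listed outcomes, so unrelated deaths and hospitalisations, apart from listed bleeding and thrombocytopenia, are not formally SAEs

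*Combined protocol and SAP*

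**What the plan says.** In Definition of Adverse Events, an adverse event counts "whether or not it is considered to be therapy related". The SAE definition that follows is narrower. It begins "An adverse event occurring while on study and considered related", explains relatedness as a reasonable possibility of causation by study treatment, and then lists four outcomes. The last of them is "Requires inpatient hospitalization, or prolongation of existing hospitalization".

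The section then extends the definition to important medical events, of which it says "These should also usually be considered serious". That extension has no relatedness wording of its own.

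Relatedness is also used in the follow-up rule: "Once the patient is removed from study, events thought to be related to the study therapy will be followed until resolution", or until a new treatment regimen starts.

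Possible Discomforts and Risk provides that all clinical events are recorded, naming among others infarctions, strokes, repeat hospitalisations and bleeding. A local committee of three faculty members not directly involved in the research evaluates them. The same section uses the term serious adverse event for a specific list (major bleeding, and thrombocytopenia below 50,000). A report of such an event leads to a committee meeting and withdrawal of antiplatelet treatment. No causality condition is attached to that list.

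**The concern.** Seriousness describes what happened to the patient; relatedness describes why. They are separate judgments, and here the first depends on the second. If the attribution of a death changes, so does its status as an SAE. The definition does not say who makes the attribution.

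The setting makes an attribution to something other than the drug plausible. Under Research design, "Loading dose administration will be given immediately after PCI as per standard of care", so effects of the procedure, the coronary disease and the study drug overlap in the hours that follow. An infarction or a prolonged stay in that window could reasonably be put down to the procedure, and it would then drop out of the SAE class.

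What is at stake is a consistent safety classification in the two arms, and anything tied to the SAE label.

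**Working it through.** The plan states no figure on this point, so the check is a reading of the clauses against each other.

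1. **Scope of the condition.** The relatedness phrase stands in the single lead-in sentence, before the list. It therefore applies to 4 of 4 outcomes.

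2. **Where the restriction enters.** The adverse event definition just above has no such condition ("whether or not it is considered to be therapy related"). The restriction arises only at the step from adverse event to SAE.

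3. **Whether the extension repairs it.** The important-medical-event clause is aimed at events that may fall short of death, immediate threat to life or hospitalisation. It does not bring unrelated deaths or hospitalisations back in. If the clause inherits the relatedness condition, the gap extends to those lesser events. If it does not, a convulsion without hospitalisation can be serious although unrelated, while an unrelated death cannot.

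4. **Whether the bleeding list repairs it.** It does so in part. Listed major bleeds, including fatal and life-threatening ones, and thrombocytopenia below 50,000 are called serious regardless of cause. Other events are not covered.

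For an event judged unrelated, the clauses give:

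| Event judged unrelated | Adverse event | SAE by the formal definition | Called serious in the risk section | Recorded and evaluated as a clinical event |
|---|---|---|---|---|
| Listed major bleed or thrombocytopenia below 50,000 | yes | no | yes | yes |
| Death from another cause | yes | no | no | yes |
| Other life-threatening event or disability | yes | no | no | yes |
| Hospitalisation or prolonged stay for another reason | yes | no | no | yes |

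5. **What depends on the label.** The one action expressly attached to a serious adverse event report is the committee meeting with withdrawal, and that has its own list. The extension clause adds: "Medical and scientific judgment should be exercised in deciding whether expedited reporting is appropriate in other situations, such as important medical events". The words on other situations suggest that the listed SAEs are the ordinary case for expedited reporting, so the label probably bears on reporting. The documents set out no reporting procedure or timeline, so this remains an inference.

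6. **Size.** Under Study Endpoints and Determination of Sample Size, "we will randomize a total of 80 patients". No serious-event rate is given, and nothing indicates how often events would be judged unrelated. An expected count would rest on an invented rate, so none is offered.

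**The case against.** The strongest reply is that only a label is at stake. Clinical events are recorded and evaluated whatever their cause, by people not directly involved in the research. The withdrawal rule has its own list without a causality condition. The endpoints are platelet reactivity in PRU and rates of high on-treatment platelet reactivity, and Possible benefits states that the study is not designed to compare clinical outcomes. Bleeding, which the protocol calls the most important adverse effect of both drugs, is largely covered by the exception. The threshold for relatedness is also low: an infarction soon after a P2Y12 loading dose could reflect inadequate inhibition and be judged related.

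Most of this stands, and it keeps the consequence modest. It does not remove the point. The plan states a rule, and that rule gives a wrong class to unrelated deaths and hospitalisations outside the list. The wording on expedited reporting suggests that the class matters.

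A reader might infer more: that unrelated deaths go unrecorded or unreported, or that no unrelated event can be called serious. The documents support neither. Recording and evaluation have no relatedness condition, no reporting procedure is given against which a failure could be shown, and the bleeding and thrombocytopenia list is a clear exception.

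**Conclusion.** The point holds as a defect in a safety definition and should be corrected. It covers all four listed outcomes when judged unrelated, except the listed bleeding and thrombocytopenia events. The effect is confined to classification and whatever follows from it; no endpoint, analysis or sample-size figure changes. The conclusion rests on reading the lead-in sentence as governing the whole list, which is its plain grammatical sense. It needs no assumption about event rates.

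**What to change.** Make these changes together:

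1. In the SAE definition, delete the relatedness condition with its parenthesis, so that the sentence runs directly from an adverse event occurring while on study to the outcomes it results in.
2. Record relatedness as a separate field, at least for every serious event, keeping the reasonable-possibility standard.
3. In Possible Discomforts and Risk, stop calling the bleeding and thrombocytopenia list a serious adverse event. Label it instead as the events that trigger committee review and withdrawal of antiplatelet treatment. Leave the list and the action as they are, and add nothing that would stop the committee from meeting for other serious events.

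The third change belongs with the first. With the broader definition alone, the withdrawal rule could be read as stopping antiplatelet treatment automatically after any hospitalisation soon after PCI.

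The cost is two wording changes, one form field and a few more events classed as SAEs. The field is a small addition: the protocol already calls for a relatedness judgment in the SAE definition and in follow-up after removal from study, but does not ask for it to be recorded separately.
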